8.5 Reporting Procedures – Notifying the Study Sponsor

The study clinician will complete a SAE Form within the following timelines:

- All serious adverse events, whether related or unrelated, will be recorded on the SAE Form and submitted to the DCC/study sponsor within 24 hours of site awareness. See Section 1, Key Roles for contact information.
- Other SAEs regardless of relationship will be submitted to the study sponsor within 72 hours of site awareness.

All SAEs will be followed until satisfactory resolution or until the site investigator deems the event to be chronic or the adherence to be stable. Other supporting documentation of the event may be requested by the DCC/study sponsor and should be provided as soon as possible.

As a follow-up to the initial report, within the following 48 hours of awareness of the event, the investigator shall provide further information, as applicable, on the unanticipated event or the unanticipated problem in the form of a written narrative. This should include a copy of the completed Unanticipated Problem form, and any other diagnostic information that will assist the understanding of the event. Significant new information on ongoing unanticipated adverse effects shall be provided promptly to the study sponsor.

The study investigator shall complete an Unanticipated Adverse Device Effect Form and submit to the study sponsor and to the reviewing IRB as soon as possible, but in no event later than 10 working days after the investigator first learns of the effect. The study sponsor contact information is provided in Section 1, Key Roles.

As a follow-up to the initial report, within the following 48 hours of awareness of the event, the investigator shall provide further information, as applicable, on the unanticipated event or the unanticipated problem in the form of a written narrative. This should include a copy of the completed Unanticipated Problem form, and any other diagnostic information that will assist the understanding of the event. Significant new information on ongoing unanticipated adverse effects shall be provided promptly to the study sponsor.

The study sponsor is responsible for conducting an evaluation of an unanticipated adverse device effect and shall report the results of such evaluation to FDA and to all reviewing IRBs and participating investigators within 10 working days after the sponsor first receives notice of the effect. Thereafter the sponsor shall submit such additional reports concerning the effect as FDA requests.

8.6 Reporting Procedures – Notifying the FDA

The study sponsor is required to report certain study events in an expedited fashion to the FDA. These written notifications of adverse events are referred to as IND/IDE safety reports.

The following describes the IND safety reporting requirements by timeline for reporting and associated type of event:

- **Within 7 calendar days** (via telephone or facsimile report)
Any study event that is:
 - associated with the use of the study drug
 - unexpected,
 - fatal or life-threatening
- **Within 15 calendar days** (via written report)
Any study event that is:
 - associated with the use of the study drug,
 - unexpected, and
 - serious, but not fatal or life-threatening

-or-

 - a previous adverse event that was not initially deemed reportable but is later found to fit the criteria for reporting (reporting within 15 calendar days from when event was deemed reportable).

The following describes the IDE safety reporting requirements by timeline for reporting and associated type of event:

- **Within 10 working days** (via telephone or facsimile report)
Any study event that is:
 - associated with the use of the study device, and
 - unanticipated,regardless of the seriousness of the event.
- **Within 5 working days** (via written report)
 - Protocol deviation to protect the life of the subject in emergency
 - Withdrawal of IRB approval
 - Lack of informed consent

Additional reporting requirements

Sponsors are also required to identify in IND safety reports all previous reports concerning similar adverse events and to analyze the significance of the current event in light of the previous reports.

Reporting Process

Adverse events may be submitted on FDA Form 3500A, or in a narrative format. If supplied as in a narrative format, the minimum information to be supplied is noted above at the beginning of section 8.3. The contact information for submitting IND safety reports is noted below:

MedWatch - Central Triage Unit
[name]
[name]
[name] or [name]

8.7 Data Safety Monitoring

The primary investigator is responsible for data safety monitoring reviews. This includes conducting systematic and periodic reviews of aggregate data and adverse events. These specific data and events include: adverse events reported following administration of medication (nebulized 3% hypertonic saline) that would include serious allergic reactions, anaphylaxis, or bronchospasms; or following administration of the device (chest percussor cup). However there are no foreseeable or specific adverse events anticipated with use of the chest percussor cup.

No predefined stopping rules will be used due to the low side effect profile of nebulized 3% hypertonic saline and chest percussion therapy and no foreseeable serious adverse events are anticipated to occur to any study participants during the duration of this study.

A summary of the outcomes of these safety reviews along with accumulated adverse events and deviations will be submitted to the IRB as part of an annual progress report at the time of the Continuing Review submission.

9 Clinical Monitoring

Clinical site monitoring is conducted to ensure that the rights and well-being of human subjects are protected, that the reported trial data are accurate, complete, and verifiable, and that the conduct of the trial is in compliance with the currently approved protocol/amendment(s), with GCP, and with applicable regulatory requirement(s).

- Monitoring for this study will be performed by the principal investigator.
- On-site monitoring will be occurring continuously while participants are participating in the study. Participants will be assessed with vital signs (temperature, heart rate, blood pressure, respiratory rate, and oxygen saturation) every 4 hours per institution protocol and as needed in addition.

10 Statistical Considerations**10.1 Statistical and Analytical Plans (SAP)**

A formal SAP will be utilized.

10.2 Statistical Hypotheses

The statistical hypotheses are as follows:

- Null hypothesis: combined nebulized hypertonic saline nebulization with chest percussion therapy in patients age 0 to 24 months admitted to the general inpatient pediatrics unit with acute bronchiolitis will not have any significant effects on primary outcomes (length of stay and number of days on supplemental oxygen therapy) and secondary outcomes (objective clinical responses included respiratory rate, heart rate, and oxygen saturation and subjective clinical responses from physicians and caregivers).
- Alternative hypotheses: combined nebulized hypertonic saline nebulization with chest percussion therapy in patients age 0 to 24 months admitted to the general inpatient pediatrics unit with acute bronchiolitis will have clinically significant effects on primary outcomes (length of stay and number of days on supplemental oxygen therapy) and secondary outcomes (objective clinical responses included respiratory rate, heart rate, and oxygen saturation and subjective clinical responses from physicians and caregivers).

10.3 Analysis Datasets

Control group: Patients meeting criteria as above prior to start date, beginning 12 months prior to start date of study, will be examined via retrospective chart review.

Experimental group: All patients meeting criteria as above beginning start date of study will be enrolled in study to receive adjuvant therapy with 3% hypertonic saline nebulization treatments combined with 3 minutes of chest physiotherapy.

10.4 Description of Statistical Methods

10.4.1 General Approach

Descriptive statistics (mean \pm standard deviation or median [25th, 75th percentiles] for continuous variables; frequencies and percentages for categorical variables) will be calculated separately by group. The two groups will be compared using the chi-square test or Fisher's exact test, as deemed appropriate, for categorical variables and the two-sample t-test or Mann-Whitney test for continuous data.

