4.2.2 Secondary Study Endpoints

The secondary study endpoints will be clinical variables including respiratory rate, heart rate, and pulse oximetry reading and these endpoints will be compared between the control and experimental group. Other secondary study endpoints will be subjective clinical impressions based on caregiver and physician report, and these endpoints will be compared between the control and experimental group. A cost-benefit analysis may also be a potential secondary study endpoint. Because data collected from surveys will reflect the pediatric patients enrolled in the study only, the parents/caregivers and physicians who answer the surveys are not considered research subjects.

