5.6 Total Number of Participants and Sites

Recruitment will end when approximately 114 participants are enrolled. It is expected that approximately 200 participants will be enrolled in order to produce 114 evaluable participants.

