7.3.2 Enrollment/Baseline

Patients enrolled in the study will be based on history and physical examination and diagnosis. No additional procedures are required to assess or confirm whether the patients still meet the eligibility criteria.

Patients, based on history, physical examination, and diagnosis, who are receiving any additional treatments or have other underlying comorbidities affecting their respiratory system will be excluded from the study.

Enrollment/Baseline Visit (Visit 1, Day 0)

- Obtain informed consent of potential participant verified by signature on study informed consent form.
- Verify inclusion/exclusion criteria.
- Obtain demographic information, medical history and medication history.
- Record vital signs, results of examinations, other assessments.
- Administer the study treatment.
- Study participants will be provided information on the continued study treatment schedule as well as the process of evaluation and surveying on response to study treatments.

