10.5 Sample Size

The proposed sample size for this study is 228 subjects ($n=114$ per group). Based on data published by Gajdos, et al., the mean duration of hospitalization for bronchiolitis recorded in the study hospitals during previous years was 6.5 days and standard deviation = 3.5 days. For a type I error of 0.05 and a power of 0.80, for detecting a 20% decrease in duration of hospitalization, a total of 228 subjects would be included (114 subjects in each group).

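### Respiratory rate, heart rate and oxygen saturation are measured at enrolment, but the planned comparison with historical controls does not adjust for the child's own baseline value

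*Combined protocol and SAP*

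**What the plan says.** Section 7.3.2 lists this item for the Day 0 visit, before the item on giving the study treatment: "Record vital signs, results of examinations, other assessments". The schedule of events (section 17) marks respiratory rate, heart rate and oxygen saturation at enrolment and again at the treatment visits. Sections 7.3.3 and 7.3.4 record the same three measures once per shift and on the day of discharge.

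Section 4.2.2 makes them secondary endpoints: "clinical variables including respiratory rate, heart rate, and pulse oximetry reading and these endpoints will be compared between the control and experimental group". Section 10.2 names them in the hypotheses.

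For the comparison, section 10.4.1 gives "the two-sample t-test or Mann-Whitney test for continuous data". Section 10.4.3 adds assumption checks, a log transformation, count models for oxygen days and a 0.05 significance level. No section names a covariate, a change from baseline, a slope, a mixed model, matching or a propensity method. The Protocol Summary describes the vital-sign endpoint as a trend after treatments, but the analysis sections do not take that up. Section 10.4.6 limits the baseline descriptives to age and gender.

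Section 10.3 defines the controls as patients from the 12 months before the start date, found by chart review. Section 10.6 says there is no randomisation or masking.

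**The concern.** In a randomised trial, leaving out the baseline value of a continuous outcome mainly costs precision. Here the cohorts come from different periods and enter by different routes. Treated children enter through parental consent (section 5.4), and those who leave early are dropped from the analysis (section 10.4.5). The protocol describes no counterpart to either step for the controls. Baseline differences can therefore be systematic.

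If one cohort starts with faster breathing or a higher heart rate, part of that difference will still be present at follow-up. An unadjusted test would read it as response to treatment, or it could mask a real response. Since baseline vital signs are not in the planned descriptive table either, a reader of the results would not see the imbalance.

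**Working it through.** **Inputs from the documents.** Section 10.5 gives 114 per group, type I error 0.05, power 0.80, a 20% decrease in length of stay, and a mean that "was 6.5 days and standard deviation = 3.5 days". The documents give no SD, effect or power target for any vital sign, no baseline/follow-up correlation and no baseline difference.

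**Assumptions.** rho is 0.3, 0.5 or 0.7, with 0.2 as a low case. The baseline difference b is 0.2 or 0.3 SD. With no treatment effect, follow-up depends on baseline by the same straight line in both cohorts, and nothing else differs between them. Tests are two-sided, and one follow-up value is taken per child.

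**1. The plan's own figure.** The difference is 0.20 × 6.5 = 1.3 days, and 1.3/3.5 = 0.371 SD. Then n per group = 2 × (1.960 + 0.842)² / 0.371² = 113.8, rounded up to 114, or 228 in total. This matches section 10.5. Sidedness is not stated; a one-sided test would need 90 per group, so the plan's figure is two-sided.

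**2. Carry-over of a baseline difference.** The bias in the unadjusted follow-up comparison is rho × b, in SD units. The standard error is √(2/114) = 0.1325. With s = rho × b / 0.1325, the false-positive rate is Φ(s − 1.96) + Φ(−s − 1.96).

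Worked case, rho 0.5 and b 0.2: bias 0.10 SD, s = 0.755, rate = 0.114 + 0.003 = 11.7%.

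| rho | b = 0.2 SD: bias, rate | b = 0.3 SD: bias, rate |
|---|---|---|
| 0.2 | 0.04, 6.1% | 0.06, 7.4% |
| 0.3 | 0.06, 7.4% | 0.09, 10.4% |
| 0.5 | 0.10, 11.7% | 0.15, 20.5% |
| 0.7 | 0.14, 18.5% | 0.21, 35.4% |

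The nominal rate is 5%.

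**3. Power.** Adjusting for baseline multiplies the residual variance by 1 − rho². The 0.371 SD effect is borrowed from length of stay purely for illustration. Power is that of a two-sample t-test with effect 0.371/√(1 − rho²) and 114 per group.

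| rho | Variance factor | Power |
|---|---|---|
| Unadjusted | 1.00 | 79.7% |
| 0.2 | 0.96 | 81.3% |
| 0.3 | 0.91 | 83.3% |
| 0.5 | 0.75 | 89.7% |
| 0.7 | 0.51 | 97.4% |

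The normal approximation gives 80.1% unadjusted and 83.6%, 89.9% and 97.5% at rho 0.3, 0.5 and 0.7.

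**4. Price of adjusting.** With a baseline difference of b, the variance of the adjusted effect rises by a factor of about 1 + b²/4. At b = 0.3 this is 1.0225, or about 2%, which is small beside the gain in step 3.

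**The case against.** The strongest reply is that the endpoint is not defined. The Protocol Summary speaks of a trend, readings are taken every shift over a stay of varying length, and a two-sample test on a within-child change or slope would already use the early readings. A reader might therefore infer that the plan certainly discards the baseline. The documents do not go that far: they never say what value enters the test. The gap stands all the same, because no change score or slope is specified, and choosing a change score would not settle the matter. Its variance is 2(1 − rho) times that of the follow-up value, so at rho 0.3 its power for the same effect is 65.9% (normal approximation), below the unadjusted test.

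Three further objections stand in part.

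- **Control baseline.** The enrolment visit exists only for treated children. That the control charts hold an equivalent reading is inferred from routine 4-hourly vital signs (sections 2.4.1 and 9). It is reasonable, but not stated.
- **Size.** The 0.37 SD effect belongs to length of stay, and one rho need not fit all three measures. Saturation in particular is bounded and is read while oxygen support is being adjusted. The average stay is given as about 1 to 5 days, so readings may be days apart and rho may be low. At rho 0.2 both the distortion and the gain are small.
- **Later planning.** Section 10.1 refers to a formal SAP, and section 1 defers analysis until a biostatistician joins. Section 1 also says that an analysis plan has been developed, and the text available contains only these tests. The deferral does leave time to pre-specify the change.

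**Conclusion.** The point holds for the secondary vital-sign endpoints. As written, the comparison uses no baseline value, and the non-randomised historical control makes that a question of bias more than of precision. How large it is cannot be read from the documents. Under the stated assumptions, the false-positive rate runs from about 6% (rho 0.2, 0.2 SD difference) to 35% (rho 0.7, 0.3 SD difference), and the power gain from under 2 points to about 18.

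A reader might infer three stronger things that the documents do not support:

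- **That the sample size is wrong.** It rests on length of stay and is reproduced exactly.
- **That the cohorts are known to differ at baseline.** No baseline data are given. The design allows a systematic difference but does not show one.
- **That baseline adjustment would make the cohorts comparable.** It removes only what the baseline reading captures. Season, age and other aspects of severity remain.

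The change should be made, but these endpoints are secondary and have no stated power, so the primary inference does not turn on it.

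**What to change.** In section 10.4.3:

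1. Set one follow-up time point or per-child summary for each vital sign, for example the reading nearest 24 hours after baseline. The model cannot be run until this is done.
2. Define baseline the same way in both arms, for example the first charted general-unit reading on supplemental oxygen and, in the treated arm, before the first study treatment.
3. Compare groups with a linear model of the follow-up value on group plus the child's own baseline value, or with a repeated-measures mixed model that has baseline as a covariate. Report the adjusted difference with a 95% interval, and keep the unadjusted comparison as descriptive.
4. State a rule for a missing baseline reading.
5. Say that confounding between the cohorts by season, age and other severity remains after this adjustment.

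In section 10.4.6, add baseline respiratory rate, heart rate and saturation by group.

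Cost: treated children need no new visit or measurement. For controls, the baseline reading must be extracted from the chart, and its availability should be checked first. Baseline timing may still differ slightly between the arms, because treated children are enrolled after consent.

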SAE	Serious Adverse Event/Serious Adverse Experience
SOP	Standard Operating Procedure
US	United States

Protocol Summary

Title	Efficacy of combined nebulized hypertonic saline and chest percussion therapy in acute viral bronchiolitis
Short Title	Combined nebulized hypertonic saline and chest percussion in pediatric bronchiolitis
Brief Summary	This study will examine the efficacy of combined nebulized hypertonic saline with chest percussion therapy in patients age 0 to 24 months admitted to the general inpatient pediatrics unit with acute bronchiolitis. 3% nebulized hypertonic saline treatments combined with 3 minutes of chest percussion therapy will be administered every 6 hours of patients selected for the study.
Phase	N/A
Objectives	Primary outcomes measured will be length of hospital stay and time on supplemental oxygen support, both to be measured in hours. The hypothesis will be that combined nebulized hypertonic saline and chest percussion therapy will decrease length of hospital stay and time on supplemental oxygen support. Secondary outcomes measured will be clinical response (respiratory rate, heart rate, pulse oximetry reading), subjective perceptions of caregivers and health care team, and cost-benefit.
Methodology	Cross-sectional quasi-experimental, open, non-randomized clinical study
Endpoint	Primary endpoints include length of hospital stay and time on supplemental oxygen therapy. Secondary endpoints include trend of respiratory rate, heart rate, and pulse oximetry reading following treatments and subjective perceptions of patients' clinical status based on caregiver and health care team.
Study Duration	12 months
Participant Duration	The duration of participation will begin from time of admission to the general inpatient pediatrics unit until time of discharge from the general inpatient pediatrics unit. This duration may vary from patient to patient, on average will last approximately 1-5 days.
Duration of IP administration	The duration of product administration will begin from time of admission to the general inpatient pediatrics unit until time of discontinuation of supplemental oxygen therapy. This duration may vary from patient to patient, on average will last approximately 1-5 days.
Population	Pediatric patients age 0 to 24 months admitted to the general pediatrics unit admitted for acute bronchiolitis requiring supplemental oxygen therapy
Study Sites	NYU Langone Hospital – Long Island, general inpatient pediatrics unit (NP5)

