2.1 Background Information and Relevant Literature

Acute bronchiolitis is a viral infection of the lower respiratory tract that primarily involves infants and young children and is only present in the pediatric population. It is the most common cause of hospitalizations in resource-rich countries. Bronchiolitis can be caused by a number of viruses, the most common being respiratory syncytial virus (RSV). [1] In the Northern Hemisphere, viral infections resulting in acute bronchiolitis increase beginning late October and will peak during the winter months of January and February and will decline through April. [2]

Bronchiolitis leads to airway inflammation, edema, and increased production of mucus. Causative viruses are spread via direct contact and inoculation at nasal mucosa or from inhalation of infective respiratory droplets. The viruses replicate in the nasopharyngeal airway and following a 4 to 6-day incubation period after transmission, the initial upper respiratory tract infection symptoms appear. Subsequent respiratory tract epithelial cell injury and necrosis occurs and this debris is aspirated into the lower respiratory tract, resulting in further inflammation, edema, and necrosis of the bronchioles, leading to airway narrowing and obstruction that is classic for acute bronchiolitis. [3]

The diagnosis of acute viral bronchiolitis is clinical, although use of molecular detection tests may help identify the causative organism. Infants and young children with acute bronchiolitis begin with upper airway symptoms of congestion, cough, and rhinorrhea that may progress to signs and symptoms of respiratory distress due to resultant lower respiratory tract obstruction such as tachypnea, accessory respiratory muscle use known as retractions, nasal flaring, grunting, or wheezing, and may also exhibit low oxygen saturations. [2] It is the resultant symptoms of lower respiratory tract obstruction that often lead to infants and young children with acute viral bronchiolitis to present to the emergency department and subsequently be admitted to the hospital.

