5.4 Strategies for Recruitment and Retention

Recruitment strategies include identifying patients upon admission to the general inpatient pediatrics unit with the primary diagnosis of acute bronchiolitis that do not meet exclusion criteria for this study. No media services will be required. If a subject requests information regarding opting out of further recruitment for all research, subjects will be directed to contact [contact] or [name].

Informed consent will be obtained at time of admission within private space of patient room and will be conducted in a sensitive manner, allowing consent to be provided in a clearly explained manner. Ample time will be provided for caregivers to decide on consent.

Information collected will be from the patient's medical chart to include age and gender. No other personal information will be required for this study. Only the primary investigator and any future added co-investigators of this study will receive this information. The target sample size for this experimental arm will be 114 patients and it is anticipated that approximately 200 patients will be screened to achieve this number. The source of participants will only be in the general inpatient pediatrics unit.

Upon patients' enrollment into the study, physicians on the patients' care team will be notified via in person or secure chat through the electronic medical record within 1 hour from patients' enrollment into the study and investigators will obtain clearance from these providers to begin the study treatments.

These physicians will also be notified at this time that they will be asked to answer subjective surveys assessing their patients' response to the study treatment. See Appendix 3.

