10.4.6 Baseline Descriptive Statistics

Baseline descriptive statistics will include participant age and gender.

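### Length of stay and oxygen days are compared with the previous year's charts without adjustment, so differences in case mix or calendar months between the two periods would be read as treatment effect

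*Combined protocol and SAP*

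**What the plan says.** The Protocol Summary describes the design as "Cross-sectional quasi-experimental, open, non-randomized clinical study". Section 10.3 defines the controls: "Patients meeting criteria as above prior to start date, beginning 12 months prior to start date of study, will be examined via retrospective chart review". The treated group is everyone eligible and enrolled from the start date.

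For the group comparison, section 10.4.1 gives "the two-sample t-test or Mann-Whitney test for continuous data", which covers length of stay. Section 10.4.2 adds a log transformation if model assumptions fail. It assigns the other primary endpoint, days on oxygen, to a Poisson, negative binomial or zero-inflated model and lists no covariates. Section 10.6, on minimising bias, says that neither masking nor randomisation is needed and offers nothing in their place.

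On baseline data, section 10.4.6 says "Baseline descriptive statistics will include participant age and gender". At the enrolment visit, section 7.3.2 requires more: "Record vital signs, results of examinations, other assessments". The Schedule of Events marks respiratory rate, heart rate, oxygen saturation and oxygen setting at enrolment. Section 4.2.2 plans to compare the three vital signs between treated and control children.

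On timing and selection, section 2.1 says that infections "will peak during the winter months of January and February and will decline through April". Section 5.6 says "Recruitment will end when approximately 114 participants are enrolled". Section 5.4 requires parental consent and adds that "investigators will obtain clearance from these providers to begin the study treatments".

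**The concern.** With historical controls, period and treatment group are the same variable. A two-sample test attributes the whole difference in mean stay to treatment, including any part caused by a milder viral season, a different age mix, a different level of oxygen support on arrival or a different spread of admission months. Its p-value and confidence interval allow only for sampling variation within each group.

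There are concrete routes by which the groups could differ without any treatment effect:

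- Control charts may come from any part of a 12-month window, while treated accrual stops when the target is reached.
- The plan fixes 114 controls and gives no rule for choosing among eligible charts.
- Treated children need a consenting family and care-team clearance; controls need neither.

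Most of the information needed to reduce the first two problems is already due to be collected, but no analysis uses it. At stake is whether a significant result for either primary endpoint can be attributed to the intervention.

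**Working it through.** **Inputs.** From section 10.5: mean stay 6.5 days, SD 3.5 days, a 20% reduction, type I error 0.05, power 0.80, 114 per group. Sidedness is not stated; two-sided is assumed. The documents give no between-period shift and no proportion of variance explained by covariates (R²), so both are assumed below and shown as ranges.

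**The plan's own figure.** Target difference = 0.20 × 6.5 = 1.3 days.

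n per group = 2 × [3.5 × (1.960 + 0.842) / 1.3]² = 113.8, rounded up to 114, or 228 in total. Power at 114 is 0.801. The stated size reproduces under the two-sided normal formula; a one-sided test would need 90 per group.

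**Standard error.** SE = 3.5 × √(2/114) = 0.464 days. A difference of 1.96 × 0.464 = 0.91 days, or 14% of 6.5, is already significant.

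**False-positive rate when treatment does nothing and the periods differ by b days.**
P(reject) = Φ(b/SE − 1.96) + Φ(−b/SE − 1.96)

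| Assumed shift b | b/SE | P(reject) |
|---|---|---|
| 0 | 0 | 5.0% |
| 0.25 days | 0.54 | 8.4% |
| 0.5 days | 1.08 | 19.0% |
| 1.0 days | 2.16 | 57.8% |

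**Shift in the other direction.** If the true effect is 1.3 days and a 0.5-day shift hides part of it, the expected difference is 0.8 days. Power = Φ(0.8/0.464 − 1.96) = 0.41, against 0.80 planned.

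**What adjustment does to power.** Scale the SD by √[(1 − R²) × VIF]. VIF is the variance inflation caused by covariates that differ between the periods; 1.0 means balanced.

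| Assumed R² | VIF 1.0 | VIF 1.1 | VIF 1.25 | VIF 1.5 |
|---|---|---|---|---|
| 0.10 | 0.84 | 0.80 | 0.75 | 0.67 |
| 0.20 | 0.88 | 0.85 | 0.80 | 0.73 |
| 0.30 | 0.92 | 0.89 | 0.85 | 0.78 |

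**What adjustment cannot do.** Suppose the whole 0.5-day shift is unrelated to the measured covariates and those covariates are balanced. The bias stays at 0.5 days while the SE shrinks to 0.464 × √(1 − R²). At R² = 0.10 the SE is 0.440 and the false-positive rate 20.6%; at R² = 0.30 they are 0.388 and 25.2%. Adjustment helps only with the part of a shift that the covariates explain.

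**The case against.** **Not every analysis is a crude two-group test.** Oxygen days get a regression model, and that model could carry covariates. This stands as a matter of wording. The plan names none, though, so as written the oxygen comparison is also unadjusted.

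**The windows may match.** The Protocol Summary gives a study duration of 12 months, so both periods nominally cover a year. Section 5.6 and section 10.6 expect about 200 enrolled to yield 114 evaluable, which could lengthen accrual (section 5.4 instead gives about 200 screened). A reader might infer that treated accrual will cover only part of a season; the documents make that possible, not certain. Year-to-year change and case mix are the firmer concerns, and matching windows would not remove them.

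**Baseline severity may not be available for controls.** Collection at enrolment is explicit only for the treated arm, and no severity score is defined. The three vital signs must be abstracted for controls because section 4.2.2 compares them. Oxygen setting is not listed for control abstraction and would have to be added.

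**A formal SAP may cover this, and the study is called a pilot.** Section 10.1 says a formal SAP will be used, but section 1 says an analysis plan has already been developed and that no biostatistician has yet been identified. Adjustment chosen after the data are in would be post hoc. Pilot or not, sections 10.2 and 10.5 set efficacy hypotheses and a powered sample size.

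**Adjustment might not help.** If the shift is unmeasured, adjustment leaves it in place and can slightly raise the false-positive rate. That stands, and it limits what the fix can promise.

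**Conclusion.** The concern holds: for a historical, non-randomised comparison, the plan specifies neither adjustment of the primary analyses nor a rule for selecting controls. Followed as written, it would report any period or case-mix difference as treatment effect, in either direction. This should be settled before outcome data are analysed.

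The error rates of about 8%, 19% and 58%, and the fall in power to 0.41, illustrate sensitivity to assumed shifts of 0.25 to 1.0 days. They are not estimates of the bias in this study, whose size and direction cannot be derived from the documents.

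Two stronger readings are tempting and unsupported. One is that the difference between periods is the largest source of error; the documents give no between-period variation from which to rank it. The other is that adjustment would reliably gain power. The 0.84 to 0.92 range needs covariates balanced between periods; with variance inflation of 1.1 to 1.5 the range is 0.67 to 0.89. The case for adjustment rests on bias, not precision.

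**What to change.** In section 10.4.2, make the primary analysis of both primary endpoints a pre-specified regression on group, adjusted for:

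- age and sex;
- first recorded respiratory rate, heart rate, oxygen saturation and oxygen setting on the unit;
- calendar month of admission.

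Use a linear model for length of stay, keeping the plan's log transformation if assumptions fail, and add the same covariates to the planned count model for oxygen days. Report adjusted effects with 95% confidence intervals and keep the crude tests as sensitivity analyses.

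In section 10.3, take every eligible control chart from the calendar months that match treated accrual, in place of an unspecified 114. Abstract the baseline values for controls at the same time point as for treated children, and add oxygen setting to the abstraction. In section 10.4.6, tabulate all these variables by group with standardised differences.

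The cost is revised wording, a modest amount of extra chart abstraction and, if the groups are imbalanced, some loss of precision, as shown above. Restricting controls to matching months could also reduce their number. The study conclusion must state that unmeasured period effects, and selection by consent and care-team clearance in the treated arm only, remain after adjustment.
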